3. GENERAL INFORMATION

Objective	To assess the efficiency of the Active Sentry handpiece at low intraocular pressure (IOP) compared with the Ozil at high IOP. The Active Sentry handpiece at low IOP (20 mmHg) is as efficient as Ozil at high (50mmHg).
Test Article(s)	Active Sentry® Handpiece
Control Article(s)	None.
Sample size	70 eyes of 35 subjects
Study Population	Subjects \geq 50 years of who are eligible to undergo sequential bilateral uncomplicated cataract surgery.
Number of sites	One
Study Design	Single site, single-masked, randomized, prospective contralateral eye study.
Masking	The data analyzer will be masked.
Variables	Primary: The total aspiration time between groups on day of surgery. Secondary: 
• Total fluid volume between groups on day of surgery.• Total phaco time between groups on day of surgery.• Total case time between groups on day of surgery.• Aspiration time during phaco between groups on day of surgery.• Central corneal thickness (CCT) between groups at postoperative day 1 and week 1.
Duration / Follow-up	Preoperative to 1 week postoperative

The study will be registered with clinicaltrials.gov.

The study will be conducted in compliance with the protocol, GCP and applicable regulatory requirements

5. INTRODUCTION

An elevated bottle height (i.e. IOP) during surgery had a significant impact post-operatively on the corneal tissue and anterior chamber.^{1,2} A recent study compared the safety and efficacy of Active Sentry (at 44-50 mmHg) handpiece with Ozil (at 65-70 mmHg) handpiece and found that Active Sentry was as efficacious and as safe.³ However, the study did not utilize the full benefit of Active Sentry, which is also being able to operate at lower IOP levels (down to 20mmhg) compared to Ozil.

6. OBJECTIVE(S)

To assess the efficiency of the Active Sentry handpiece at low IOP compared with the Ozil at high IOP.

7. SUBJECTS

7.1. *Subject Population*

Eligible test subjects will be 50 years of age or older and who are eligible to undergo sequential bilateral uncomplicated cataract surgery.

A total of 70 eyes of 35 subjects at one site will be enrolled. Both eyes of a subject must be enrolled. Subjects must meet the inclusion criteria. Prior to enrollment, subjects will be provided information on the study and asked to sign a patient information and consent form to participate. The patient information and consent form will be approved by an appropriate ethics committee.

7.2. *Inclusion Criteria*

Subjects are eligible for the study if they meet the following criteria:

Note: Ocular criteria must be met in both eyes.

- Be eligible to undergo sequential bilateral uncomplicated cataract surgery.
- Undergo uneventful cataract surgery.
- Gender: Males and Females.
- Both eyes must have same grade of cataract.
- Willing and able to provide written informed consent for participation in the study.
- Willing and able to comply with scheduled visits and other study procedures.

7.3. *Exclusion Criteria*

If any of the following exclusion criteria are applicable to the subject or either eye, the subject should not be enrolled in the study.

- Patient under 50 years of age.

- Unable to complete sequential bilateral cataract surgery in both eyes by the same surgeon (JS).
- Patient cataract surgery complicated by posterior capsular tear.
- Any disease state deemed by PI that increases risk of complicated cataract surgery (ie Pseudoexfoliation syndrome, zonular dehiscence, history of eye trauma, RA, prior refractive surgery, etc).

The principal investigator reserves the right to declare a patient ineligible or non-evaluable based on medical evidence that indicates they are unsuitable for the trial.

Pregnancy has a known effect on the stability of refractions and visual acuity. As such, subjects who become pregnant during the study will not be discontinued but their data may be excluded from analyses of effectiveness.

8. STUDY DESIGN

8.1. Study Design

This study is a single site, single-masked, randomized, prospective, contralateral eye study of the efficiency of the Active Sentry handpiece at low IOP compared with the Ozil at high IOP. Subjects will be assessed pre-operatively, operatively and at 1 day and 1 week post-operatively. Clinical evaluations will include measurement of visual acuity and central corneal thickness (CCT).

The primary outcome measure will be the total aspiration time between groups on day of surgery.

Secondary outcome measures are as follows:

- Total fluid volume between groups on day of surgery.
- Total phaco time between groups on day of surgery.
- Total case time between groups on day of surgery.
- Aspiration time during phaco between groups on day of surgery.
- Central corneal thickness (CCT) between groups at postoperative day 1 and week 1.

Exploratory outcome measures are as follows:

- Cumulative dissipated energy between groups on day of surgery.

8.2. Methods Used to Minimize Bias

As a randomized study there is no expected bias. Patient selection will be based on the patient's interest and the surgeon's opinion as to whether they are a suitable candidate for sequential bilateral cataract surgery. The data analyzer will be masked.

The measurement of visual acuity will be conducted in a systematic fashion to minimize bias. Individuals conducting visual acuity measures will be instructed to perform the same testing in the same fashion for all subjects, with the same level of encouragement to subjects.

All data collection will be completed through provided Case Report Forms (CRFs) or computer files generated by automated test equipment. All site personnel involved in the study will be trained in regard to conducting study-specific procedures.

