9.3.1. Central Corneal Thickness (CCT)

Central corneal thickness (CCT) will be measured by Pentacam or equivalent. The same methodology of assessing CCT should be consistent for each subject.

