9.3.2. Slit Lamp Examination

The current standard for quantifying anterior segment inflammation is clinical slit-lamp examination findings classified using the Standardisation of Uveitis Nomenclature (SUN) grading system.

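### Section 8.2 says randomisation leaves no bias to expect and masks only the analyst, so staff measuring CCT, acuity and inflammation after surgery may know the handpiece: a modest gap, cheap to close

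*Combined protocol and SAP*

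**What the plan says.** Section 8.1 describes the design: "This study is a single site, single-masked, randomized, prospective, contralateral eye study". The synopsis (Section 3) and Section 8.2 both name the one masked role: "The data analyzer will be masked". Section 8.2, the section on minimising bias, opens with "As a randomized study there is no expected bias". It then sets out controls: standardised acuity testing ("Individuals conducting visual acuity measures will be instructed to perform the same testing in the same fashion for all subjects"), an equal level of encouragement, training of site personnel, and data capture on CRFs or in files from automated equipment.

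After surgery, Sections 9.2.3 and 9.2.4 require CCT, slit-lamp examination and acuity at day 1 and week 1 for each eye. The methods are in Section 9.3. For CCT: "Central corneal thickness (CCT) will be measured by Pentacam or equivalent", with one method kept throughout for each subject. For the slit lamp: "clinical slit-lamp examination findings classified using the Standardisation of Uveitis Nomenclature (SUN) grading system". For acuity: a Snellen chart. None of these sections, nor Table 15.1, says who performs the measurement or whether that person is masked. Section 8.1 lists "Central corneal thickness (CCT) between groups at postoperative day 1 and week 1" as a secondary outcome.

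**The concern.** Randomisation makes the two groups of eyes comparable at the start. It does nothing about detection bias, where a person who knows the treatment measures or grades differently. The masked analyst takes no measurements, so masking that role does not address this either.

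The expected direction is written into the plan. Section 5 gives as background that high pressure during surgery affects the cornea and anterior chamber. An examiner who knows which eye was operated on at low pressure could lean towards a thinner cornea or a quieter chamber in that eye. At stake is the credibility of the CCT comparison and of the descriptive acuity and inflammation summaries. Masking cannot be added once the data are collected.

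**Working it through.** No figure in the plan bears on this point, and the Section 11 sample size does not change with it. The check is a comparison of sections.

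**1. Who is masked.** The design is single-masked, and the synopsis and Section 8.2 both give that one role to the analyst. Sections 9.2.3, 9.2.4, 9.3.1 to 9.3.3 and Table 15.1 add no other. The plan as written therefore provides no masking of postoperative examiners. It does not say that they are told the handpiece; it is silent.

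**2. Which measures are exposed.**

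| Measure | When | Status | Open to a postoperative examiner's knowledge? |
|---|---|---|---|
| Total aspiration time | Surgery | Primary | No |
| Fluid volume, phaco time, case time, aspiration time during phaco | Surgery | Secondary (4) | No |
| Cumulative dissipated energy | Surgery | Exploratory | No |
| CCT | Day 1, week 1 | Secondary (1) | Somewhat: instrument reading, but an unspecified equivalent device is allowed |
| Visual acuity | Day 1, week 1 | Not a listed outcome | Yes |
| Slit-lamp SUN grade | Day 1, week 1 | Not a listed outcome | Yes |

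Listed outcomes: 1 primary + 5 secondary + 1 exploratory = 7. Exposed: 1 of 7, namely CCT. Acuity and SUN grade enter only through the general summaries in Section 10.2.

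**3. How many measurements.** 35 subjects × 2 eyes × 2 postoperative visits = 140 planned eye-visits (visits 3, 4, 3a and 4a). This counts measurements taken without stated masking; it does not measure bias.

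**4. What the existing controls do.** Uniform acuity instructions and encouragement, staff training and a constant CCT method within each subject reduce variation between examiners and devices. In a contralateral design the last of these covers both eyes. None of them conceals the handpiece. Section 8.2 also standardises encouragement in order to limit bias, which sits badly with its own statement that none is expected.

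**5. Size.** The documents give no expected CCT difference, no CCT standard deviation and no information on examiner effects, so no magnitude can be computed. By the nature of the measures, any bias should be smallest for an automated CCT reading and larger for SUN grade and acuity.

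**The case against.** The strongest reply is that this is little more than a wording fault. The objective is efficiency, the only specified test is on aspiration time (Section 10.2), and no CCT hypothesis or margin exists. CCT is an instrument reading, and the more subjective measures support no listed outcome. All of that stands, and it limits the weight of the point. It does not rescue the sentence in Section 8.2, and CCT remains a declared between-group comparison.

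Some stronger readings are tempting but unsupported:

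- *That the primary result is compromised.* It is recorded at surgery, where postoperative staff have no influence. One surgeon operates on both eyes and is not listed as masked. That may be the larger risk of bias for aspiration time, but it is a separate matter that masking examiners would not address.
- *That CCT carries the trial's claim of clinical benefit.* Section 5 is background, and Section 19.2 does not rest its benefit statement on CCT.
- *That the examiner compares two eyes side by side.* Section 9.2 schedules first-eye and second-eye visits separately, on separate CRFs.
- *That examiners will see the operative record.* Operative data are on CRFs 2 and 2a, apart from the postoperative forms. Access is neither granted nor barred.

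A practical objection also stands. Adverse events are recorded on each CRF (Section 13), and the investigator must judge their relation to the device (the causality subsection within Section 13.3). A blanket rule hiding the assignment would obstruct that judgement.

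**Conclusion.** The point holds in a limited form. The statement that no bias is expected is wrong as methodology, and the plan leaves postoperative measurers free to know the handpiece. The consequence is confined to one secondary outcome, CCT at day 1 and week 1, and to acuity and SUN grades that are summarised only. The primary outcome and the other four secondary outcomes are not affected by it.

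This rests on two assumptions: that no masking provision exists outside the available text, and that postoperative staff could learn the assignment in ordinary clinic work. If the site already keeps it from them, one sentence in Section 8.2 settles the matter. The change is worth making because it is cheap and must be in place before data collection, not because the trial's main conclusion depends on it.

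**What to change.** In Section 8.2:

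- Delete the statement that no bias is expected.
- State that the surgeon is not masked.
- State that the existing staff who measure CCT and acuity at visits 3, 4, 3a and 4a, and who grade the slit lamp where the grader is not the surgeon, are not told the handpiece assignment or IOP setting.
- Keep assignment and IOP setting off the measurement pages of CRFs 3, 3a, 4 and 4a, and file operative CRFs 2 and 2a separately.
- Record on the CRF whether the slit-lamp grader was the surgeon.
- State that the investigator keeps access to the assignment for adverse event causality and patient care.

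The cost is protocol wording, a CRF layout rule and separate filing. Sample size, visits and analysis do not change. That existing staff can do this is an assumption, since the documents give no staffing. The slit-lamp grade stays unmasked wherever the surgeon does the grading.

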9. STUDY PROCEDURE

9.1. *Informed Consent / Subject enrollment*

No subject will be enrolled into the study who does not meet the inclusion/exclusion criteria and does not sign the current approved informed consent document. Informed consent will be obtained prior to collecting any data for the study. The original signed documents will be maintained by the investigator as a permanent part of the subject's medical records. A signed copy will be provided to the subject.

9.2. *Visits and Examinations*

Subjects will participate in 7 study visits, including one visit for screening. Visits will include an uptake visit, two operative visits, and 4 postoperative visit (Visit numbers 1-4 and 2a, 3a, and 4a below). The visit schedule, complete with window and associated CRF forms, are displayed in Table 9.2-1. Details of each study visit, including testing to be conducted, are provided below.

Table 9.2-1. Visit Schedule

Visit Number	Visit Name	Visit Window	CRF Number
1	Preoperative	-90 to 0 days from surgery	1
2	Operative	0 from surgery	2
3	1 Day Postoperative	1-2 days postoperative	3
4	1 Week Postoperative	7 days (± 3) postoperative	4
2a	Operative*	0 from surgery	2a
3a	1 Day Postoperative*	1-2 days postoperative	3a
4a	1 Week Postoperative*	7 days (± 3) postoperative	4a

*second eye

9.2.1. Preoperative

At the preoperative exam, subjects will be consented, qualified for the study (compared with inclusion/exclusion criteria), and assigned a study ID/subject number. Subject numbers will be assigned sequentially at each site in the order of enrollment. Pre-operative qualification should take place no more than 90 days prior to surgery.

A medical history will be taken and exams will include the tests described below:

- visual acuity,
- slit lamp examination,
- central corneal thickness

In addition, all site-specific, routine, usual standard of care preoperative measures should be undertaken.

Measurements should be made as described in section 9.3 below.

9.2.2. Operative (Surgery)

All subjects will undergo sequential bilateral cataract surgery. The surgeon's usual standard of care with regard to treatment and medication will be used for all study subjects. Surgery planning will be performed using the surgeon's preferred method.

Surgical findings will be recorded and will include the tests below:

- Total phaco time,
- Total aspiration time,
- Total fluid volume,
- Total case time,
- Cumulative dissipated energy

Any adverse events/serious adverse events (AEs/ SAEs) occurring during surgery will be noted at this visit. Any other problems during surgery and comments regarding surgery will be documented.

Any subject whose surgery is not completed successfully will be documented in the appropriate case report form. These subjects will be monitored for safety but clinical performance data may be excluded from the analysis.

9.2.3. Postoperative 1 Day

All routine, usual standard of care postoperative measures should be undertaken. In addition, the subject will undergo central corneal thickness measurement, slit lamp examination, and VA testing in accordance with the specifications below (Section 9.3). Adverse events will be monitored.

9.2.4. Postoperative 1 Week

All routine, usual standard of care postoperative measures should be undertaken. In addition, the subject will undergo central corneal thickness measurement, slit lamp examination, and VA testing in accordance with the specifications below (Section 9.3). Adverse events will be monitored.

9.2.5. Exit Procedures

In the event of premature exit from the study, all study related examinations should be completed where possible. The Exit CRF should be completed, noting that the subject did not complete the study and the reason for premature study exit. If no premature exit from the study occurs, the Exit CRF should be completed at the end of Visit 7 (Postoperative 1 Week, Second Eye).

9.3. Study Methods and Measurements

All routine testing and basic eye examinations should be carried out at each study visit. Abnormalities should be recorded in the CRF “Comment” section. Specific study examination procedures are outlined below.

9.3.1. Central Corneal Thickness (CCT)

Central corneal thickness (CCT) will be measured by Pentacam or equivalent. The same methodology of assessing CCT should be consistent for each subject.

9.3.2. Slit Lamp Examination

The current standard for quantifying anterior segment inflammation is clinical slit-lamp examination findings classified using the Standardisation of Uveitis Nomenclature (SUN) grading system.

9.3.3. Visual Acuity (VA)

Measure target distance visual acuity using a high contrast Snellen chart under photopic lighting at a distance of 20 ft for eyes targeted for distance and 14-16 inches for eyes targeted for near.

9.4. Unscheduled Visits

Unscheduled exams may be conducted at the discretion of the Investigator with all relevant information from the exam recorded in the source documents and on the Unscheduled Visit pages within the CRF booklet.

9.5. Discontinued Subjects

Discontinued subjects are those who do not have an exit visit or who come into the office to be exited prior to the scheduled final study visit. Subjects may be discontinued from the study at any time if, in the opinion of the investigator, their continued participation in the study poses a risk to their health. The reasons for discontinuation include:

- a. Adverse event;
- b. Lost to follow-up;
- c. Subject decision unrelated to an adverse event;
- d. Protocol violation;
- e. Treatment failure;
- f. Other.

To ensure the safety of all subjects who discontinue prior to Visit 7, investigators should assess each subject and, if necessary, advise them of any therapies and/or medical procedures that might be needed to maintain their health. Any changes in medical health and/or use of concomitant medications should also be captured.

10. ANALYSIS PLAN

10.1. Analysis Data Sets

All subjects who are enrolled in the study will be evaluated for safety. Efficacy analyses will be performed based on data from those eyes where uncomplicated cataract surgery was completed.

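### The efficacy set is built by eye and no paired method is named, so unmatched fellow eyes can enter the aspiration-time comparison and shift it

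*Combined protocol and SAP*

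**What the plan says.** Four places bear on a subject whose surgery goes wrong, or does not happen, in one eye.

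- **Section 10.1** defines the efficacy set by eye: "Efficacy analyses will be performed based on data from those eyes where uncomplicated cataract surgery was completed". It does not mention the fellow eye.
- **Section 7** works by subject. Section 7.1 states "Both eyes of a subject must be enrolled". Section 7.2 adds "Note: Ocular criteria must be met in both eyes" and lists "Undergo uneventful cataract surgery" as an inclusion criterion. Section 7.3 opens with "If any of the following exclusion criteria are applicable to the subject or either eye, the subject should not be enrolled in the study"; its list includes "Patient cataract surgery complicated by posterior capsular tear" and inability to complete both surgeries with the same surgeon. These outcomes are known only at or after surgery. Section 7.3 also says "The principal investigator reserves the right to declare a patient ineligible or non-evaluable".
- **Section 9.2.2**, on subjects whose surgery is not completed successfully, says: "These subjects will be monitored for safety but clinical performance data may be excluded from the analysis". It gives no criterion for when.
- **Section 10.2** tests the difference between groups against 23 s. It names neither a paired test, nor a complete-pair requirement, nor a model for incomplete pairs.

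**The concern.** A contralateral design removes differences between patients only if each patient contributes both eyes or neither. Suppose a patient with a difficult lens has long aspiration times in either eye and the Active Sentry eye is complicated. Section 10.1 read literally drops that eye and keeps the same patient's slow Ozil eye. If the group means are then compared without pairing, a complication on the test handpiece moves the estimate towards non-inferiority. A complication on the Ozil eye moves it the other way.

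Half-pairs can arise within the plan. The two eyes are operated on at separate visits (2 and 2a). Section 18.3 terminates, without replacement, a subject with a severe adverse event that may be related to the study. If that happens after a clean first surgery, one eye qualifies under section 10.1 and the other does not exist.

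Timing matters as well. Aspiration time is recorded at surgery and only the data analyzer is masked (section 8.2). The optional wording in section 9.2.2 and the investigator's right to declare a patient non-evaluable therefore leave the choice open after the times are known.

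**Working it through.** **Inputs from section 11:** SD 36.8 s, true difference 0 s, margin 23 s, power 80%, significance level 5% (sidedness not stated), 32 per group, 35 subjects recruited.

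**Assumptions, because the documents give no figures:** number of half-pairs k = 1 to 3 (3 = 35 − 32, the whole dropout allowance); patient-level excess D = 18.4 to 36.8 s (0.5 to 1 SD); inter-eye correlation 0.3, 0.5 or 0.7.

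**Step 1. The plan's own figure.** The independent-groups formula at one-sided 5% gives n = 2 × 36.8² × (1.645 + 0.842)² / 23² = 31.7, so 32 per group, as stated. One-sided 2.5% gives 40.2, so 41. A paired calculation at one-sided 5% gives 32 only if the inter-eye correlation is zero; at 0.3, 0.5 and 0.7 it gives 23, 16 and 10 pairs. The sample size was thus computed as if the eyes were independent, which makes an unpaired analysis a realistic reading of section 10.2.

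**Step 2. Size of the shift.** Let k subjects lose the eye on one handpiece. The other handpiece keeps 35 eyes, k of them D seconds slower, so its mean rises by k × D/35. The handpiece that lost eyes has no such term.

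| k | D = 18.4 s | D = 36.8 s | Share of 23 s margin |
|---|---|---|---|
| 1 | 0.5 s | 1.1 s | 2% to 5% |
| 2 | 1.1 s | 2.1 s | 5% to 9% |
| 3 | 1.6 s | 3.2 s | 7% to 14% |

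In complete pairs the patient term cancels and this shift is zero. It is also zero if D = 0 or if the losses split evenly.

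**Step 3. Effect on the claim.** Simulation with 40,000 trials per setting, pooled t, upper limit of the two-sided 95% interval at most 23 s, k = 3, correlation 0.5, true difference 0:

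| Setting | Chance of claiming non-inferiority |
|---|---|
| No patient excess | about 78% |
| D = 36.8 s, Active Sentry eyes lost | 88% |
| D = 36.8 s, Ozil eyes lost | 59% |
| Paired interval, 32 complete pairs | 93% |

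**Step 4. False claims.** Same analysis, true difference 23 s, the three Active Sentry eyes lost, D = 36.8 s:

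| Correlation | Two-sided 95% | One-sided 5% |
|---|---|---|
| 0.3 | 2.5% | 5.6% |
| 0.5 | 1.2% | 3.2% |
| 0.7 | 0.2% | 1.2% |

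An unpaired interval on correlated eyes is too wide, and this absorbs the shift. With no inter-eye correlation it is not absorbed: a normal approximation gives 5.4% with the two-sided 95% interval. That case is unlikely for two eyes of one patient with the same cataract grade and the same surgeon.

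**The case against.** **Section 7 does not remove anyone from the analysis.** A reader might infer three flatly contradictory rules, with section 7 discarding the whole subject. Its words concern enrollment. Because some criteria can be judged only after enrollment, removal from analysis is an inference. One can also read the sections in sequence, with section 7 settling eligibility and section 10.1 then the analysis set, so that no half-pair survives. The triggers also differ: a tear or an eventful operation in section 7, surgery not completed successfully in 9.2.2, surgery not both uncomplicated and completed in 10.1. This stands. The text is ambiguous about the fellow eye, and nothing resolves it.

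**A paired test would drop the single eyes by itself.** This is true, and it is the natural analysis for this design. Most of the gain, from about 78% to 93% at correlation 0.5, comes from pairing and not from the fellow-eye rule. But no paired test is specified, and the sample size does not assume one.

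**The three-half-pair case stacks assumptions.** It spends the entire dropout allowance on one-eye losses. If each loss is equally likely on either handpiece, all three fall on one with probability 2 × (1/2)³ = 25%, and in a given direction 12.5%. At correlation 0.5 the between-subject SD is 36.8 × √0.5 = 26 s, so D = 36.8 s is 1.4 of those. High-risk eyes are excluded. This stands: the one-half-pair row is the more ordinary case.

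**Inflated false non-inferiority.** A reader might infer this from the 88% figure. That figure is the chance of a correct claim at a true difference of 0; Step 4 shows no material excess over 2.5% at correlations of 0.3 to 0.7.

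**Conclusion.** The point holds as a defect of specification. As written, the plan can put unmatched fellow eyes into the primary comparison, and it does not say whether they belong there. The shift is small for one half-pair (0.5 to 1.1 s) and modest for three on one handpiece (1.6 to 3.2 s, at most 14% of the margin). It requires an unpaired or eye-level analysis, losses unbalanced between handpieces, and affected patients who are slower than the rest. The harm is a biased estimate, a chance of success that depends on which eyes are lost, power given up by not pairing, and an exclusion decision open after the times are known.

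The documents do not support the stronger conclusion that the trial would falsely declare non-inferiority. Nor should complete pairs be called unbiased without qualification: they remove the unmatched-eye shift, but still select on a surgical outcome that the handpiece could itself affect. The correction should be made before the data are seen.

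**What to change.** In sections 10.1 and 10.2, state that:

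- the primary comparison of total aspiration time uses within-subject differences (Active Sentry minus Ozil) in subjects with both eyes in the efficacy set;
- if one eye is not in that set, the fellow eye is left out of the primary comparison but kept in listings and safety;
- a sensitivity analysis fits a mixed model with a subject random effect to all randomized eyes with a recorded aspiration time, including complicated eyes where it was recorded;
- complete pairs remove the unmatched-eye shift but not selection on surgical outcome.

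In section 9.2.2, replace the optional exclusion with a reference to section 10.1. Make section 7 refer to the same rule for criteria known only at surgery. Apply the rule to the secondary surgical outcomes.

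The cost is a few sentences and one model. A few single eyes leave the primary analysis, and the 32 pairs of section 11 remain only if total losses, for any reason, do not exceed 3 subjects. Pairing more than repays this: with 32 pairs the chance of a claim at a true difference of 0 is 93% at correlation 0.5 and 83% at 0.3, against about 78% and 74% for the unpaired eye-level analysis with no patient excess.
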